## **11. CLINICAL EVALUATIONS**

### **11.1. Demographics (Screening Visit)**

The demographic data will consist of: subject study number, sex, age, race, ethnicity, height, weight, body mass index, and child-bearing potential for females.

### **11.2. Medical and Medications History (Screening Visit/Baseline Visit)**

Medical history and concurrent diseases will be reviewed. History will be obtained from interview and review of medical records. History of analgesic use will be elucidated, an appropriate wash-out period will be prescribed and Baseline Visit will be scheduled for the end of this period, and within 14 days of the screening visit.

### **11.3. Concomitant Medications (All Visits)**

Any therapies for other diseases that are considered necessary for the subject's welfare may be given at the discretion of the Investigator. All concomitant therapy used during the study, should be recorded in the CRFs by the name (generic name for pharmacological therapy), the start and end date, and indication.

Acetylsalicylic acid up to 325mg per day is allowed during the study as thrombosis prophylaxis. Acetylsalicylic acid for analgesic purposes is not allowed. The prohibition for taking any analgesic 24 hours before a visit also applies.

No other product under investigation may be used concomitantly with the Investigational Product.

### **11.4. Non-pharmacological treatment (All Visits)**

Non- pharmacological therapy will be noted in the CRF. This may include but are not limited to:

- resting the shoulder joint
- physical therapy
- range-of-motion exercises
- appropriate application of ice and moist heat
- patient education
- self-management programs
- personalized social support through telephone contact
- aerobic and muscle-strengthening exercises
- occupational therapy
- joint protection and energy conservation

- assistive devices for activities of daily living

New therapies may not be initiated during the study. See [Appendix 2](#) .

### **11.5. Physical Examination of Shoulder (All Visits)**

The physical examination of the study shoulder at screening will include assessment for joint inflammation seen as joint effusion and/or tenderness on palpation. The skin over the study shoulder will also be observed for any infection.

### **11.6. Pregnancy Test (Baseline Visit)**

At the Baseline Visit, a urine pregnancy test should be performed for all women of childbearing potential to be processed locally. A positive result excludes the subject from the study. No other mandatory clinical chemistry or hematology tests will be performed during this study.

## 12. ASSESSMENT OF EFFICACY

The choice of outcome measures in this study is based on recommendations on measures to be used in clinical studies on OA of the shoulder. Effectiveness assessments will be completed by subjects at each scheduled study visit at Week 6, Week 12, Week 18 and Week 26 after the injection visit.

The primary efficacy assessment will be the VAS (0-100mm) shoulder pain on movement. A Visual Analog Scale (VAS) is a measurement instrument that measures a characteristic or attitude that is believed to range across a continuum of values and cannot be objectively recorded. A VAS is a horizontal line, 100mm in length, anchored by word descriptors (i.e., no pain, worst pain imaginable) at each end. For this study, the subject will mark the line at the point that they feel represents their perception of his or her pain in the last 24 hours. The VAS score is determined by measuring in millimeters from the left end of the line to the point that the subject marks (Burckhardt, et al., 2003; Johnson, 2005; Paul-Dauphin, et al., 1999)

The secondary efficacy variables will include the VAS (0-100mm) shoulder pain at night, American Shoulder and Elbow Surgeons patient self-evaluation (VAS pain today and activities of daily living only), ASES physician ROM assessment, and PGA. In addition to the efficacy assessments described above, the consumption of rescue medication will be accessed.

In this study the SPOM, SPAN, ASES patient self-evaluation (VAS pain today and activities of daily living only) and PGA are completed by the patient at each study visit. The ASES physician ROM is completed by the Investigator. The same evaluating investigator should preferably see the patient at all visits in order to present the questionnaires for the patient in a uniform way throughout the study. If more than one investigator has assessed any patient at any time-point during the study, it should be documented in the CRF.

At baseline all efficacy assessments have to be performed before the study product is injected. All assessments should be made without comparing the data from the assessments at previous visits.

### 12.1. Shoulder Pain on Movement (SPOM) VAS (0-100mm) (All Visits)

The SPOM VAS (0-100mm) scale will be completed both for the study shoulder and the untreated shoulder on the screening visit to exclude significant pain on the contralateral shoulder that might affect pain assessments.

The self-administered SPOM VAS (0-100mm) scale will contain the instruction below for the subject:

“How severe has your pain on movement been in the last 24 hours? Place a vertical mark in the line below to indicate how severe your pain has been.”

## **12.2. Shoulder Pain at Night (SPAN) VAS (0-100mm) (All Visits)**

The self-administered SPAN VAS (0-100mm) scale will contain the instruction below for the subject:

“How severe has your pain at night been in the last 24 hours? Place a vertical mark in the line below to indicate how severe your pain has been.”

## **12.3. American Shoulder and Elbow Surgeons (ASES)**

In 1993 the American Shoulder and Elbow Surgeons society (ASES) adopted a standardized form for the assessment of shoulder function. The ASES form contains a patient self-evaluation section and a physician assessment section. The form is used to measure baseline shoulder function and is applicable to all subjects regardless of their diagnoses.

### **12.3.1. ASES Range of Motion (ROM) (Screening, Baseline, Week 6, Week 12 and Week 26)**

The ASES physician-administered ROM will contain instructions for the assessment of the subject's shoulder active range of motion (measured in degrees) for the movements of abduction, extension, forward elevation, external rotation, internal rotation, cross-body adduction will be taken using a 41 cm universal goniometer.

### **12.3.2. ASES Patient Self-Evaluation (All Visits)**

The ASES patient self-evaluation (PSE) portion contains a VAS for pain today and instability and a questionnaire for activities of daily living (ADL). In this study, patients will only complete the VAS pain today and activities of daily living only sections of the patient self-evaluation form. The ADL questionnaire is marked on a four-point ordinal scale that can be converted to a cumulative ADL index. A Shoulder Score Index (SSI) can then be derived from the VAS pain today score and the cumulative ADL score.

The patient self-evaluation section consists of eleven items divided into two areas:

1. Pain (one item): The question asked is: “How bad is your pain today?” the patient's response to the pain today question is marked on a 0-10cm (equal to 0-100mm) VAS scale anchored with verbal descriptors at 0 (No pain at all) and 100mm (Pain as bad as it can be).

2. Function (ten items): the items in the function area assess activities of daily living (1. put on a coat, 2. sleep on your painful or affected side, 3. wash back/do up bra in back, 4. managing toilette, 5. comb hair), demanding activities (6. reach a high shelf, 7. lift 10 pounds above shoulder, 8. throw a ball overhand) and general activities (9. do usual work, 10. do usual sport). The possible responses are 0 (unable to do), 1 (very difficult to do), 2 (somewhat difficult), and 3 (not difficult).

#### **12.4. Patient Global Assessment (PGA) (All Visits)**

The VAS Patient Global Assessment (PGA) asks a patient to rate on a scale how they feel overall. The scale goes from 0 (zero) to 10. Only the two extremes have text: level 0 is defined as “Very poor” and level 100 as “Excellent”.

The self-administered PGA will contain the instruction below for the subject:

“Considering all the ways your target shoulder affects you, how are you doing today?”

The subject should mark the alternative that he/she finds appropriate (Pincus, et al., 1989).

#### **12.5. Recorded Use of Rescue Medication**

Subjects will be advised to take acetaminophen as rescue medication for study shoulder pain as required. Acetaminophen intake will be recorded in the shoulder pain rescue medication diary which will be transcribed on the CRF.

### **13. ASSESSMENT OF SAFETY**

All AEs which occur during the course of the subject's involvement in the clinical investigation shall be appropriately recorded and reported to ensure their continuing safety. The Medical Devices Regulations SOR/98-282 and the Guidance Document for Mandatory Problem Reporting for Medical Devices provides guidance for Post-Market Vigilance Reporting and sets out specific requirements for the management of AEs. Each type of AE is subject to different reporting requirements.

All AEs must be followed until they are resolved or the study has ended. In addition, all serious, as well as, non-serious AEs with a causal relationship to the device under investigation and/or its usage must continue to be followed until resolved or until the Investigator assesses them as chronic or stable, even if the subject's participation in the study is otherwise completed. See [Appendix 3](#) for more details.

## **14. STATISTICS**

### **14.1. Methods**

#### **14.1.1. General**

There is a single pre-planned hypothesis test for the primary variable. There are no pre-planned hypotheses tests for secondary or exploratory efficacy variables or safety variables. Any inferential statistic for these variables is exploratory. All variables will be summarized using descriptive statistics such as sample size, mean, standard deviation, median, minimum and maximum and frequencies, i.e. counts and percents. All other analyses details will be described in a statistical analysis plan (SAP).

#### **14.1.2. Safety**

The incidences of all AEs and serious AEs, complaints and complications will be monitored for all subjects that signed an informed consent. However, safety analysis shall be carried out on those subjects that were enrolled into the study and received the DUROLANE 3mL injection (the Safety Population). Since this is a single arm study there are no inter-group comparisons. Nevertheless, all events will be reviewed by the Investigator and categorized in terms of both severity and the likelihood that these events were caused as a result of using DUROLANE 3mL. Enrollment will be paused for thorough review in the event of any serious AE deemed to be as a direct result of using the treatment.

Below are general considerations for summary and display of AEs and concomitant medications. Additional safety analyses will be described in a SAP.

#### **Adverse Events**

- AEs will be coded using the current MedDRA dictionary.
- All AEs will be summarized by MedDRA primary system organ class (SOC) and preferred term (PT). If a subject has more than one occurrence of the same preferred term then they will be counted only once in a summary table for that preferred term.
- A listing by subject of all AEs will be provided. Listings of serious AEs and AEs leading to discontinuation will also be provided.

#### **Concomitant Medications**

- Concomitant medications will be coded using the WHO dictionary.
- All concomitant medications will be summarized by WHO generic term. If a subject has more than one occurrence of the same generic term then they will be counted only once in summary tables for that generic term.
- A listing by subject of all concomitant medications will be provided.

**Physical Exams (*performed as needed*):**

- A listing by subject of all abnormal physical exams will be provided.

**14.1.3. Efficacy****14.1.3.1. Primary Variable**

VAS (0-100mm) SPOM over weeks 0, 6, 12, 18 and 26

**14.1.3.2. Primary hypothesis**

Ho: VAS SPOM over weeks 6, 12, 18 and 26  $\geq$  VAS SPOM at week 0 (baseline)

Ha: VAS SPOM over weeks 6, 12, 18 and 26  $<$  VAS SPOM at week 0 (baseline)

**14.1.3.3. Primary hypothesis statistical test method**

A mixed effect repeated measures (MERM) regression will be used. VAS SPOM will be the dependent variable. The weeks 0 (baseline), 6, 12, 18, and 26 visits will be a fixed effect covariate. Subjects will be random effects. The correlation structure will be unstructured. If convergence is problematic then an alternative covariance structure will be necessary. A contrast will be constructed to test the hypothesis of a VAS SPOM reduction from baseline.

**14.1.3.4. Trial success criteria**

If the weeks 6, 12, 18, and 26 VAS SPOM least square mean versus week 0 (baseline) VAS SPOM least square mean contrast achieves the 0.05 type I error level of statistical significance this trial will be considered a success.

The mean VAS result at baseline is estimated to be 60 mm and that, a reduction in VAS result of 25%, i.e., 15 mm, will be achieved. The magnitude of the improvement in VAS was assumed to be equal between successive time points, i.e. the VAS results of 60, 55, 50 and 45 mm are expected at baseline, and Weeks 6, 12, 18 and 26, respectively.

The magnitude of what is considered a minimally clinically meaningful change from an individual patient perspective has been cited in the literature as 10-22% from baseline to endpoint following a given treatment as reported on the VAS instrument (Erich, et al., 2000; Dworkin, et al., 2008; Angst, et al., 2002). In this context, the established trial success criteria of a 25% reduction in pain from baseline values represents a clinically meaningful change in patients' pain as it exceeds this threshold range.

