## Primary hypothesis:

Ho: VAS SPOM over weeks 6, 12, 18 and 26  $\geq$  VAS SPOM at week 0 (baseline)

Ha: VAS SPOM over weeks 6, 12, 18 and 26  $<$  VAS SPOM at week 0 (baseline)

Primary hypothesis statistical test method:

A mixed effect repeated measures (MERM) regression will be used. VAS SPOM will be the dependent variable. The weeks 0 (baseline), 6, 12, 18, and 26 visits will be a fixed effect covariate. Subjects will be random effects. The correlation structure will be unstructured. If convergence is problematic then an alternative covariance structure will be necessary. A contrast will be constructed to test the hypothesis of a VAS SPOM reduction from baseline.

Trial success criteria:

If the weeks 6, 12, 18, and 26 VAS SPOM least square mean versus week 0 (baseline) VAS SPOM least square mean contrast achieves the 0.05 type I error level of statistical significance this trial will be considered a success.

Secondary variables:

*The weeks 0, 6, 12, 18 and 26:*

- SPAN VAS (0-100mm)
- ASES patient self-evaluation (PSE) Shoulder Score Index (SSI): (range: 0-100)
- PGA VAS (0-100mm)
- Shoulder pain rescue medication consumed (unit: average mg per week)

*The weeks 0, 6, 12, and 26:*

- ASES physician assessment (PA) range of motion (ROM): 5 questions (right and left, active and passive; total 10 assessments) (unit: degrees)

Exploratory ASES variables (patient self-evaluation only):

*The weeks 0, 6, 12, 18 and 26:*

- ASES PSE pain today: VAS (range: 0-10cm)
- ASES PSE activity of daily living: 10 questions (range: 0,1,2,3)

Safety variables:

Over the entire study:

- MedDRA coded adverse events
- WHO coded concomitant medications
- Physical exams (range: 0,1,2,3)

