**Sample Size:**

The sample size was estimated for a repeated measures ANOVA using method MOT2 in nQuery Advisor 7.0 statistical software. A sample size of 29 will be capable of detecting a reduction in mean VAS pain on movement score of 15 mm (25% reduction from a baseline mean of 60mm) over the course of the study with 80% power under the following assumptions:

Type I error rate, $\alpha$ ,	= 0.05
Standard deviation within time point	= 25 mm
Correlation between visits	= 0.5
Mean VAS (0-100mm) results at:	
0 weeks (baseline)	= 60 mm
6 weeks	= 55 mm
12 weeks	= 50 mm
26 weeks	= 45 mm

A minimum of 36 subjects will be enrolled into the study to allow the power of the study to be maintained in the case of a drop-out rate of up to 20%.

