## 14.2. Sample Size Considerations

The sample size was estimated for a univariate one-way repeated measures ANOVA using method MOT2 in nQuery Advisor 7.0 statistical software. A sample size of 29 will be capable of detecting a reduction in mean VAS pain on movement score of 15 mm (25% reduction from a baseline mean of 60mm) over the course of the study with 80% power under the following assumptions:

Type I error rate, $\alpha$ ,	= 0.05
Standard deviation within time point	= 25 mm
Correlation between visits	= 0.5
Mean VAS (0-100mm) results at:	
0 weeks (baseline)	= 60 mm
6 weeks	= 55 mm
12 weeks	= 50 mm
26 weeks	= 45 mm

Hence, when the sample size is 29, a single-group repeated measures analysis of variance with a 0.05 significance level will have at least 80% power to detect a difference in means across the 4 time-points for the individual subjects characterized by an effect size of 0.1 (i.e., a Variance of means,  $V = \sum(\mu_i - \mu)^2 / M$ , of 31.25, a standard deviation at each time-point of 25 mm, and a constant between time-point correlation of 0.5).

Assuming a 20% drop-out rate a minimum of 36 subjects will be enrolled to maintain 80% power. It is noted that the sample size estimation does not include the week 18 time point.

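### Section 14.1.3.4 calls a 25% pain reduction the trial's success criterion, but the success rule requires only p<0.05 against zero reduction and never tests 25%

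*Protocol*

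**What the plan says.** The decision rule is stated twice in the same terms. The Synopsis begins it with "If the weeks 6, 12, 18, and 26 VAS SPOM least square mean versus week 0 (baseline) VAS SPOM least square mean contrast", and section 14.1.3.4 completes it: if that "contrast achieves the 0.05 type I error level of statistical significance this trial will be considered a success". Section 14.1.3.2 sets the null as no reduction, with no margin ("Ho: VAS SPOM over weeks 6, 12, 18 and 26" at or above the baseline value). Section 14.1.1 adds: "There is a single pre-planned hypothesis test for the primary variable".

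The 25% figure appears in two roles.

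- **Planning value.** Section 14.2 says "A sample size of 29 will be capable of detecting a reduction in mean VAS pain on movement score of 15 mm", that is 60 to 45 mm, with 45 mm placed at Week 26. The Synopsis says the same. Earlier in 14.1.3.4 it is likewise an expectation.
- **Success criterion.** The last sentence of 14.1.3.4 says that "the established trial success criteria of a 25% reduction in pain from baseline values represents a clinically meaningful change", because 25% exceeds a cited range of 10-22%. The section describes that range as an individual patient's change from baseline to endpoint.

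**The concern.** Section 14.1.3.4 contains a rule with no effect-size threshold and a sentence saying that the threshold is 25%. They differ in three ways:

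1. **Threshold.** The rule asks for a reduction greater than zero, not 25%.
2. **Quantity.** The 25% is a Week 26 value; the contrast averages four follow-up visits.
3. **Benchmark.** The 10-22% range concerns individual patients; the contrast is a group mean.

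What is at stake is the claim attached to a pass. This is a single-arm, open-label study done as a post-approval commitment (section 5.1) and meant to support the EU indication (section 5.2). Section 5.2 also reports that in the cited saline-controlled trial every group, saline included, improved from baseline. A reduction greater than zero is therefore a modest bar, and the clinical-relevance sentence carries much of the interpretation. As written, a reduction near 10% with p<0.05 could be reported as meeting a pre-specified 25% criterion. Conversely, a significant 17% result could be said to have failed it.

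**Working it through.** **Inputs.** From section 14.2: SD 25 mm, correlation 0.5, means 60, 55, 50 and 45 mm at Weeks 0, 6, 12 and 26, alpha 0.05, n = 29. From section 7.2: 36 enrolled, up to 29 evaluable. The sidedness of the contrast test is not stated, so both are shown. Assumed here: complete data, equal correlation across all five visits including Week 18, and a t test on n-1 degrees of freedom.

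**1. Reproducing the stated sample size.** The variance of the four means is (7.5² + 2.5² + 2.5² + 7.5²)/4 = 31.25. The effect size is 31.25/(625 × 0.5) = 0.1. With noncentrality n × 4 × 0.1 and 3 and 3(n-1) degrees of freedom, power is 0.791 at n = 28 and 0.807 at n = 29. The stated 29 is correct for the test it was computed for.

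**2. Expected size of the tested quantity.** Section 14.2 gives no Week 18 mean ("It is noted that the sample size estimation does not include the week 18 time point"), so it is taken as 50 to 45 mm.

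- Week 18 = 50: 60 - (55 + 50 + 50 + 45)/4 = 10.0 mm (16.7%).
- Week 18 = 45: 60 - (55 + 50 + 45 + 45)/4 = 11.25 mm (18.8%).

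Section 14.1.3.4 lists four means for five visits, with equal steps. Equal steps from 60 to 45 (60, 56.25, 52.5, 48.75, 45) give 9.375 mm (15.6%). Continuing 5 mm steps to 40 mm at Week 26, which contradicts section 14.2, gives 12.5 mm (20.8%). All these readings are below 25%.

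**3. Smallest observed reduction that passes.** The per-subject contrast variance is 25² × (1 - 0.5) × (1 + 1/4) = 390.6. The SE is √(390.6/n): 3.67 mm at n = 29 and 3.29 mm at n = 36. The critical reduction is t(n-1) × SE.

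| Correlation | n | One-sided 0.05 | Two-sided 0.05 |
|---|---|---|---|
| 0.5 | 29 | 6.24 mm (10.4%) | 7.52 mm (12.5%) |
| 0.5 | 36 | 5.57 mm (9.3%) | 6.69 mm (11.1%) |
| 0.3 | 29 | 7.39 mm (12.3%) | 8.90 mm (14.8%) |
| 0.3 | 36 | 6.59 mm (11.0%) | 7.91 mm (13.2%) |
| 0.7 | 29 | 4.84 mm (8.1%) | 5.82 mm (9.7%) |
| 0.7 | 36 | 4.31 mm (7.2%) | 5.18 mm (8.6%) |

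**4. Check on the baseline SD.** With entry at 50 mm or more (section 7.4.2) and a mean of 60 mm on a 0-100 scale, baseline variance cannot exceed (60 - 50) × (100 - 60) = 400, so the SD is at most 20 mm. With baseline SD 20, follow-up SD 25 and correlation 0.5, the contrast variance is 400 + 625 × (1 + 3 × 0.5)/4 - 2 × 0.5 × 20 × 25 = 290.6. The critical reductions are then 5.39 and 6.48 mm (n = 29) or 4.80 and 5.77 mm (n = 36), that is 8.0% to 10.8%.

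**5. What the estimate would show.** Two-sided 95% CIs at the planning SD and correlation:

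| Observed average reduction | n = 29 | n = 36 |
|---|---|---|
| 10.0 mm | 2.5 to 17.5 mm | 3.3 to 16.7 mm |
| 11.25 mm | 3.7 to 18.8 mm | 4.6 to 17.9 mm |

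These intervals exclude zero and include 15 mm. Such a result would pass the rule without establishing 25%.

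**The case against.** The strongest reply is that nothing operative is wrong. The hypotheses, the test and the success rule agree wherever they appear, and the observed means will be reported beside the p-value and would expose an overstatement. Any trial powered at 80% for a planning value reaches significance at a smaller observed effect. Against the protocol's own 10-22% range, the gap is also smaller than the contrast with 25% suggests: the smallest passing reduction at the planning values (9.3% to 12.5%) is near its lower end, and the expected 16.7% to 18.8% lies inside it. On timing, 60 to 45 mm at Week 26 is itself a baseline-to-endpoint change. Finally, the text alone cannot show whether the sponsor mislabelled a planning value or left a second criterion out of the rule.

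Much of this stands as a limit on severity: alpha, power and the decision are untouched, and the critical values only illustrate the point. The timing reply holds for the Week 26 planning value but not for the averaged contrast that decides success. A passing result may well be clinically relevant, but passing does not establish that, and the sentence says it does. On intent, the rule, the zero null, the single test and the sizing all treat 25% as a planning value; only this sentence does not.

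**Conclusion.** The concern holds and should be fixed. The last sentence of 14.1.3.4 names a success criterion that the rule does not contain, and rests the clinical-relevance claim on it. Under the planning SD and correlation, an observed average reduction of 9.3% to 12.5% of baseline is enough to pass, depending on n and sidedness; correlations from 0.3 to 0.7 widen this to 7.2% to 14.8%. The expected value of the tested contrast is itself below 25% on every reading of the planned means. These sizes depend on the stated variance assumptions and the assumed Week 18 mean, but the contradiction in the text does not. The harm is confined to what a pass may be said to show.

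**What to change.** Replace the last sentence of section 14.1.3.4 with wording such as:

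> *The 15 mm (25%) reduction is the planning value at Week 26 used for the sample size; it is not a success criterion. p<0.05 on the contrast shows only a mean reduction from baseline greater than zero; clinical relevance is judged separately from the contrast estimate and its 95% CI.*

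This adds no test, endpoint or threshold. The estimate and interval come from the model already planned, and data collection, alpha, sample size and the pass/fail rule stay as they are. The cost is one sentence of protocol wording, and a bare p<0.05 will support a less favourable claim.
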